# BOSS-Covid-19 Study (BOSS-001)

study arms controlling for other factors of interest such as gender, baseline viral load, age etc. The interaction of the study arm with these covariates will be also investigated. Considering the small size of the study, number of covariates to be added to such multivariable models will be limited. We expect that only 2-3 covariates will be added to these models in addition to the study arm.

## **5.3.5 Covariate and Subgroup Analyses**

Covariate and subgroup analyses will be presented when applicable and supported by the available data, considering that the sample size of each study arm is already limited by up to 30 subjects per arm.

## **5.3.6 Safety Analyses**

Safety will be evaluated by summary of adverse events. Adverse event incidence rates will be summarized for each study arm, namely, Active Drug and Placebo Arms, in terms of severity and its relationship to study drug. A tabulation of Serious Adverse Events (SAEs) will be provided within each study arm with the number of patients experiencing a given AE or ADE, and the number of episodes while on study. Similar reports will be generated for AE monitoring purposes for the entire study cohort without unblinding of the study participants while the study is still ongoing.

# **6 Definitions for Clinical Evaluations**

## **6.1 Follow-Up Time Points**

The treatment time for each participant is 14 days and the follow-up time is for 7 days or until ongoing adverse events are resolved up to 45 days as part of safety follow-up.

## **6.2 Points of Enrollment**

Subjects will be considered enrolled in the study when they have been informed of all aspects of the study, had ample time to review the Informed Consent document, signed the Informed Consent document, satisfied the Inclusion/Exclusion Criteria, and randomized.

## **6.3 Definitions for Clinical Evaluation**

Clinical evaluation will be done using Flu-Pro Plus questionnaire modified for Covid-19 patients treated in an outpatient setting. The participants will fill out the questionnaire at the time of Screening, Enrollment, and from Day-1 to Day-21 post randomization each day using online data capture forms.

# BOSS-Covid-19 Study (BOSS-001)

## 7 General Considerations

If a subject is not able to complete the study after being enrolled, the Investigator, or designee will document the last contact with the subject. All attempts to contact the subject will be documented in the source documentation. Missed or out-of-range visits will be considered protocol deviations.

### 7.1 Missing Data and Outliers:

In this study, the primary objective is driven by data collected during the baseline visit and up to Day-21; considering the short treatment and follow-up time, missing data is expected to be minimal. We do not anticipate excessive missing values; however, missingness structure will still be analyzed as to whether or not the missingness is Missing Completely at Random (MCAR), or Missing at Random (MAR), or Not-Missing at Random (NMAR). In the event of MCAR and MAR, sensitivity analyses will be carried out by using Multiple Imputation (MI) techniques when appropriate. Specifically for the Modified FLU-PRO Plus data, Last-Value-Carried-Forward (LVCF) imputation approach will be utilized as this assessment will be for Day-1 through Day-21 and LVCF approach would be appropriate to impute intermittent missing values in these time series type data.

The data quality checks will be an ongoing effort for the study and potential outliers will be detected and resolved as much as possible while the study is ongoing. In the analysis phase, the outliers will be evaluated based on whether or not they are influential values in given statistical model a given outlier may be perfectly in line with the model built and does not necessarily mean problematic for modeling assumptions. If they are found to be influential, then possible data transformation approaches such as log-transformation will be considered.

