9.4 STATISTICAL ANALYSES

9.4.1 GENERAL APPROACH

Categorical variables will be presented as frequencies and percentages with column and row percentages in 2x2 or Rx C tables as appropriate. Association between two nominal variables will be investigated using Chi-Square tests and/or Fisher's Exact test as needed. Cochran Armitage trend-test may be included among the possible tests to investigate the possible trend between one ordinal factor and one binary factor. Association between two ordinal variables may be investigated through Non-zero Correlation test. Continuous variables will be presented as mean and standard deviation as well as five-number summary (minimum, first quartile, median, third quartile, and maximum). Range and inter-quartile range may also be explicitly provided as needed. Distribution of a continuous variable among the levels of a binary or polynomial factor will be investigated graphically through boxplots and through Wilcoxon-MannWhitney test and/or Kruskal Wallis tests. Association between two continuous variables will be described through scatter plots and Pearson's and Spearman's correlation coefficients as appropriate. When needed, normality assumption of a given continuous variable will be tested using Shapiro-Wilk Normality test. The details of the statistical models addressing each and every primary, secondary, and exploratory objectives along with primary predictors and control variables will be provided in a corresponding Statistical Analysis Plan (SAP). In this protocol document, a general analysis and statistical testing approach will be provided, and the details will be left for the study SAP.

In all comparisons and tests, a two-sided p-value will be used and a Type-1 error rate of 0.05 will be used to indicate significance. No multiplicity correction will be employed for statistical tests addressing the two primary objectives. Similarly, no multiplicity correction will be employed for statistical tests addressing the secondary and exploratory objectives as the results from these objectives must be considered within the hypotheses generating context.

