9.4.2 ANALYSIS OF THE PRIMARY EFFICACY ENDPOINT(S)

The primary endpoint of this clinical trial is the estimate of the median time to sustained clinical response for the treatment and placebo arms. Kaplan-Meier method will be used to estimate the time to sustained clinical response distribution and log-rank test will be utilized to compare the time to sustained clinical response distributions between the two study arms. Events will be defined as cases that attain clinical response while on the follow-up window and time to event will be calculated as the days from symptom onset to the resolution of symptoms to zero based on the Modified FLU-PRO Plus questionnaire. Patients who do not attain to clinical response while on the follow-up window will be censored on Day-21 or on the day they are off study before Day-21 due to other reasons. Although all analyses will be conducted based on the intent-to-treat context, sensitivity analyses based on the adherence to the protocol regimen will also be carried out for the primary as well as secondary objectives.

When appropriate, Last-Value-Carried-Forward (LVCF) imputation approach will be utilized for the missing values. As this is a small study that has a short span of enrollment and treatment windows, we do not anticipate excessive missing values; however, missingness structure will still be analyzed as to whether or not the missingness is Missing Completely at Random (MCAR), or Missing at Random (MAR), or Not-Missing at Random (NMAR). In the even of MCAR and MAR, sensitivity analyses will be carried out by using Multiple Imputation (MI) techniques.

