# BOSS-Covid-19 Study (BOSS-001)

at least three days. Time to sustained clinical response will be calculated from the date of testing to the first day all symptoms are  $\leq 2$ .

Power calculation will be based only on the first primary objective of the trial. Based on the median time to sustained clinical response reported by CDC [122], the expected median time to response in the placebo arm will be approximately 16 days from the onset of symptoms in outpatients. With a sample size of 20 in each arm, a difference in median time to sustained clinical response of 10 days between the intervention arm and the placebo arm will be able to be detected with 81.5% statistical power with 5% Type-1 error rate. Median time to sustained clinical response will be estimated based on 21-day follow-up. With an attrition expectation of around 20%, the planned accrual is 26 patients in each arm and potentially up to 30 patients.

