## Analysis plan for Secondary Aim-3:

Secondary estimand-3 is defined to be the difference of total and subdomain symptom scores measured through Modified FLU-PRO Plus questionnaire between participants taking 3 g TQ Formula (500 mg per capsule, 3 capsules BID) and participants taking placebo regardless of whether or not they actually receive their assigned therapy (ITT) and assuming that their hospitalization and treatment discontinuation rates will be similar. To address this estimand, the differential change of total and subdomain symptom severity score measured by Modified FLUPRO Plus overtime between the two-study arm will be estimated and compared between the two study arms. As the total and subdomain symptom severity score will be measured at Baseline (Day-1) and on each day through Day-14, the outcome variables of interest will be a longitudinal interval-scale measures. To assess the differential behaviour of total and subdomain symptom scores overtime between the two study arms, Random Coefficients Models will be utilized where total and each of the subdomain symptom severity score will be the dependent variables and study arm and time will be main predictors. Total and subdomain symptom severity scores may be subjected to some data transformation (e.g., log transformation) to improve the model fit and assumptions as necessitated by model diagnostics. In addressing this objective, all available data will be utilized; that is, in addition to the evaluable patients, data from non-evaluable patients such as data only at baseline visit or data just at baseline and Day-10 for example will be used to improve the local fit of the underlying model. To assess differential behavior in total symptom severity score, time\*study-arm interaction will be investigated as well. When scientifically indicated, aggregated symptom severity scores may be defined through combining a set of subdomains such as Nose, Eyes, And Throat. The above mentioned intercurrent events are applicable for Secondary estimand-1 as well. Therefore, hospitalization-free, while-on-study and per-protocol treatment versions of the above estimand will also be considered within each population definitions above. For the above analyses, the MIXED procedure of SAS software will be utilized.

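### SAP 7.1 prescribes LVCF for the symptom diary without exempting the Aim-3 mixed models, which need no imputation under MAR; depending on how it is read, it can distort the slope difference in either direction.

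*SAP*

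**What the plan says.** SAP 7.1 (Missing Data and Outliers) states: "Specifically for the Modified FLU-PRO Plus data, Last-Value-Carried-Forward (LVCF) imputation approach will be utilized as this assessment will be for Day-1 through Day-21". The sentence goes on to justify the method as suitable for intermittent missing values in a daily series. It does not say what happens after a participant's last diary, or which analyses use the filled data. The same section expects little missing data and foresees multiple imputation as a sensitivity analysis.

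Protocol 9.4.2 is broader and more conditional: "When appropriate, Last-Value-Carried-Forward (LVCF) imputation approach will be utilized for the missing values". Protocol 10.1.8 repeats it. Neither mentions intermittent gaps.

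SAP 5.3.3, Secondary Aim-3, compares total and subdomain symptom scores over Days 1–14 in all randomised participants. It uses a random coefficients model in PROC MIXED, with the time-by-arm interaction also examined. Incomplete participants are kept: "data from non-evaluable patients such as data only at baseline visit or data just at baseline and Day-10 for example will be used".

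SAP 3.2 (Sample size) plans accrual "With an attrition expectation of around 20" per cent. SAP 7.4 says that sensitivity analysis does not apply to this study, although SAP 7.1 and 5.3.2 both plan some.

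**The concern.** A programmer could follow SAP 7.1 and fill every series, or follow the Aim-3 text and fill none. The two give different estimates, and no passage chooses between them.

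Filling brings no benefit here. A likelihood-based mixed model uses incomplete series directly and, under MAR with a correct mean model, needs no imputation. LVCF freezes the score at its last value in an illness where scores are expected to fall, and the model then treats the carried values as observed. If Aim-3's own examples were filled to Day 14, a baseline-only participant would become 14 identical scores with slope zero. A participant with diaries on Day 1 and Day 10 would acquire 12 values nobody reported (Days 2–9 and 11–14).

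At stake is the treatment difference in symptom decline, for the total score and every subdomain. This point does not concern how the primary event is derived.

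**Working it through.** **Plan figures.** The documents give no figure for the effect of LVCF. The input used is the 20% attrition: 20/0.8 = 25 per arm, against the planned 26. Its timing and split by arm are not stated, so both are assumed below, as are the recovery curves.

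**Method.** With balanced daily data, the time-by-arm estimate equals the difference between arms in mean per-participant least-squares slope over Days 1–14. The mean day is 7.5 and Σ(t − 7.5)² = 227.5. For linear decline with last diary on day k, carried to Day 14, the fraction of true slope kept is

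r(k) = Σ (t − 7.5)·min(t, k) / 227.5.

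This gives r(1) = 0, r(4) = 0.154, r(7) = 0.446, r(10) = 0.758 and r(13) = 0.971. The average over k = 1 to 13 is 0.462.

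**Equal dropout, carried to Day 14.** With 20% dropout in each arm, evenly spread, the fraction of the slope difference kept is 0.8 + 0.2 × 0.462 = 0.892, a shrinkage of 10.8%. If the 20% is spread over 21 days, 20% × 14/21 = 13.3% have left by Day 14, and shrinkage is 13.3% × 0.538 = 7.2%.

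The same calculation for other curves and timings, at 20% per arm, gives this percentage shrinkage (a negative value means enlargement):

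| Recovery (active v placebo) | Last diary evenly over Days 1–13 | Days 1–4 | Days 5–9 | Days 10–13 |
|---|---|---|---|---|
| Linear | 10.8 | 18.7 | 11.0 | 2.5 |
| Exponential, half-lives 6 v 16 days | 7.7 | 17.0 | 6.1 | 0.6 |
| Exponential, 4 v 6 | 1.5 | 12.5 | −4.1 | −2.5 |
| Exponential, 3 v 8 | 1.0 | 11.9 | −4.8 | −2.5 |

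**Unequal dropout, linear, evenly spread, slopes 2.5 v 1.5 per day.**
- 10% active, 30% placebo: 2.5 × (1 − 0.1 × 0.538) − 1.5 × (1 − 0.3 × 0.538) = 2.365 − 1.258 = 1.108, so the true difference of 1 is enlarged by 10.8%.
- 30% active, 10% placebo: 2.096 − 1.419 = 0.677, a shrinkage of 32.3%.
- No true effect: a 20-point dropout gap creates a spurious difference of 0.20 × 0.538 = 10.8% of the common slope. In 250 simulated trials with assumed SDs and 30% v 10% dropout, the test rejected in 11.2% with LVCF and 4.8% with observed diaries.

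**Interior gaps only.** With 10–30% of interior diaries missing at random and the first and last days observed, the difference changes by about 0.2% or less under linear decline. Under curved recovery (6 v 16) it is enlarged by 1.5–5%.

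**Check in the planned type of model.** In 60 simulated trials (26 per arm, linear decline, 20% dropout in each arm), the mean slope difference was −1.008 with complete data, −1.004 with observed diaries and −0.924 with LVCF carried to Day 14. That is about 8% shrinkage with a Monte Carlo error of about 3 points, consistent with 10.8%. Observed diaries alone showed essentially none.

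**The case against.** The strongest reply is that the SAP never orders values to be carried past the last diary. The only purpose SAP 7.1 gives for LVCF is intermittent gaps. The Aim-3 text describes baseline-only participants entering the model as they are. Read together, the two could mean observed diaries with at most interior gaps filled, and then the bias is small. The protocol adds the condition that LVCF be appropriate, and its 9.4.2 sentence sits under the primary endpoint. The 20% is a sample-size allowance, SAP 7.1 expects minimal missing data, and diaries are still requested after treatment discontinuation or hospitalisation. Aim 3 is secondary, and protocol 9.4.1 treats secondary results as hypothesis-generating.

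Much of this stands. A reader might infer that every dropout will become a flat line and that the treatment difference will shrink by at least 10%. The documents do not support that: filling the tail is one reading of unclear text, and 10% is not a floor. Nor is the bias always toward no effect when dropout is equal, as the negative entries in the table show. Power loss is not a safe claim either. It appeared in simulations under linear decline but not under exponential decline.

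What does not stand is the idea that the text already settles the matter. The reason given for a method does not limit where it is applied, and the protocol has no such limit. Even on the narrow reading, the Day 1 and Day 10 participant would receive eight carried values (Days 2–9). Reminders after discontinuation or hospitalisation do not recover diaries lost to withdrawal or loss to follow-up.

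**Conclusion.** The concern holds as an unresolved conflict with an avoidable bias, not as a bias of fixed size. SAP 7.1 prescribes LVCF for the diary, Aim-3 describes a model on incomplete series, and nothing says which data the model receives.

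If LVCF runs past the last diary, with 20% dropout in each arm evenly spread over Days 1–14, shrinkage is about 11% for linear decline and 1–8% for the curved recoveries tried. Across dropout timings the range is about 19% shrinkage to 5% enlargement. Unequal dropout can create a difference or distort one in either direction. If LVCF is confined to interior gaps, the effect is under 0.5% (linear) to about 5% enlargement (curved). Only the 20% comes from the plan. Trajectory shape, dropout timing, split by arm and the simulation SDs are assumptions.

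Observed-diary analysis has its own limit: a linear-time model can be somewhat off if recovery is curved. For exponential decline at assumed rates of 0.12 v 0.06 per day, LVCF shrank the complete-data difference by 7.0%. In 80 simulated trials, some with convergence warnings, the observed-diary model overstated it by about 5%. The case for observed diaries is therefore clearest when the time trend is modelled adequately. Overall this is a cheap improvement to a secondary analysis.

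**What to change.** - In SAP 7.1 and in SAP 5.3.3 Aim-3, add: *Total and subdomain scores in the Secondary Aim-3 models are analysed from observed diaries only, by likelihood (PROC MIXED) under MAR. LVCF is not applied.* Say also that the all-available-data sentence in Aim-3 means diaries actually completed.
- Align protocol 9.4.2 and 10.1.8 with this.
- Keep LVCF, if wanted, only as a labelled supplementary run, stating whether it fills interior gaps or also days after the last diary.
- Reconcile SAP 7.4 with the sensitivity analyses in SAP 7.1 and 5.3.2.

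The cost is wording, with less programming than LVCF and no new data, visits or participants. The downside is that standard errors will reflect the missing diaries. The shape of the time trend also needs checking, and the model diagnostics and transformations already foreseen for Aim-3 give a place to do that.

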### 7.2 Protocol Violations and Deviations

Missed visits and out of range visits will be considered protocol deviations while such participants will still be deemed evaluable for the primary objective. Investigators will not deviate from the clinical protocol except to deliver emergency care or to eliminate an immediate hazard to the subject. All study deviations from the clinical protocol will be captured in the study CTMS database. All deviations with the potential to affect subject safety, rights, or well-being will also be reported as required by the IRB/EC and to sponsor.

### 7.3 Disposition of Subjects and Withdrawals

All subjects who provide informed consent and are enrolled will be accounted for in this study. Subjects maintain the right to discontinue their participation in the study at any point. If a subject

# BOSS-Covid-19 Study (BOSS-001)

exercises this right, the Investigator will make every effort to ascertain and document the reason for withdrawal.

## 7.4 Sensitivity Analysis

Sensitivity analysis is not applicable for this study.

## 7.5 Changes to Planned Analysis after Blind Review of Data and Unblinding Consideration (if Applicable)

Not applicable.

## 7.6 Interim Analysis and Data Monitoring

There is no planned interim analysis for the primary objective of the study; however, there will be safety interim analyses after the initial cohort of 12 patients have been enrolled and have received at least one dose of the assigned drug. This safety interim analysis will be conducted without unblinding the patients. As part of this safety interim analysis, if two or less number of patients in this initial cohort of 12 patients experience Grade 3+ adverse events attributable to the study regimen and not resolved through symptomatic treatments within 48 hours, there will be no need for unblinding the safety cohort; however, if there are 3 or more cases with Grade 3+ adverse events attributable to the study regimen and not resolved through symptomatic treatments within 48 hours, the enrollment will be halted, this initial cohort of patients will be unblinded to evaluate the distribution of the AEs between the placebo and the study drug, and the possible corrective amendments will be considered.

## 7.7 Timing with Respect to Database Locking

The data quality checks will be an ongoing effort while the study is still on. When all patients are enrolled and complete their modified Flu-Pro Plus assessment to Day 21, a complete data extraction will be requested for an efficacy data quality control. Once the efficacy data is deemed to be complete and accurate, the efficacy data will be locked and another complete data extraction will be requested to generate a preliminary efficacy report. As part of this preliminary efficacy analysis, the study statistician will be unblinded but all other member of the study team will remain blinded and the preliminary safety report will not contain any individual level data. Upon the completion of the 45-day safety follow-up of the last enrolled patient, there will be a final data quality assessment finalizing the safety parameters, generating final set of queries for the study sites to correct/modify/update. Once all data quality check queries are adequately addressed, the study database will be ordered to be locked and the entire study team will be unblinded to patient randomization.

# BOSS-Covid-19 Study (BOSS-001)

## 7.8 Analysis Software

All analysis will be performed using SAS® Software version 9.4 or later. When appropriate, Rpackage will be used as well.

## 7.9 List of Tables, Figures and Listings

Demographic characteristics table, AE and SAE tables, tables of Covid-19 test results both from the rapid test and RT-PCR, the distribution statistics table for the viral load assessments, any other secondary objective measure tables. Modified FLU-PRO Plus assessments will be shown graphically as time series plot with a reference line at Level-2 ('Somewhat') where the y-axis will show the scale from 'Not at all (Level-0)' to 'Very much (Level-4)'.

